part of the procedure as well as the total procedure time, and reduce the number of recurrences by long term follow-up.

Purpose:

The purpose of this study is to investigate surgical work space and surgical conditions in patients scheduled for laparoscopic umbilical, -linea alba and incisional herniotomy. The patients will act as their own control with evaluation of surgical work space and surgical conditions during both deep NMB and no NMB.

Hypothesis:

Deep NMB defined as TOF=0 and post-tetanic count (PTC) ≥ 1 , will give better surgical workspace, better surgical conditions, as well as shorter duration of surgery and reduced number of recurrences of hernias compared with no NMB.

Method:

See appendix 1, flow diagram.

Design:

Randomized, cross-over design, with blinding of patient and surgeon. Randomization is used to determine the treatment sequence (no NMB followed by deep NMB (Group A) or deep NMB followed by no NMB (Group B)) in order to blind the surgeon.

Outcomes:

Primary outcome:

Improvement of surgical workspace (rated on a 5-point scale) estimated as the difference between the workspace during deep NMB and the workspace without NMB. Ratings are performed in the same patient during stable pneumoperitoneum at 12 mmHg.

Protocol
The hernia study
September 16. 2016

Secondary outcomes: (comparing Group A with Group B)

- Surgeon's rating of surgical conditions while suturing the hernia (5-point rating scale)
- Duration of operating time (from first incision to last suture)
- Assessments if the surgical space is better, unchanged or worse when evaluating before and after the intervention
- Number of sudden contractions of the abdominal wall during operation (bucking or coughing),
- Number of insufflator alarms where pneumoperitoneum > 17 mmHg,
- Number of episodes with continuous abdominal contractions where the abdomen feels "tight" but the operation can still proceed (the intestines are gradually displaced near the inner surface of the abdominal wall).
- Number of recurrences of hernias by 2 year follow-up (separate publication). Patients will 2 years after operation receive a letter with invitation to ambulatory clinical assessment by a surgeon at Herlev Hospital or have the opportunity to receive a visit by a surgeon at their home address.

Number of patients:

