Responsible for patient information and declaration of consent is local investigator. The patient will receive oral and written information about the project.

The initial contact with the patient will be done at a preoperative surgical evaluation at Herlev Hospital. The surgeon conducting the evaluation will handout the written patient information to all patients planned to have laparoscopic ventral-hernia surgery at Gentofte Hospital. The patient will at the same time receive a short oral information about the study and will be informed that the local investigator will contact the patient by telephone within a few days. This gives the patient time to read the information and to discuss it with family or relatives. The patient will be offered the possibility of being accompanied by a family member or another person at the telephone information interview. The local investigator will answer any question regarding the study and check that the inclusion criteria are met and none of the exclusion criteria are found. The patient will be offered a face-to-face interview if he/she wish. The patient will be informed that he/she will receive usual treatment if he/she does not want to participate, and that participation is voluntary, and that he/she always has the right to disclaim consent without affecting the further treatment.

After a period of consideration, depending on the patient's needs, an attempt will be made to obtain consent.

Pre-operative assessment:

In the Case Report Form (CRF) the following baseline data is noted:

Age

Weight

Height

Sex

BMI

Protocol
The hernia study
September 16. 2016

ASA group (I-IV)

Previous abdominal surgery

Co-morbidity which requires daily medical treatment

Parity

Randomization:

Randomization is 1:1, and done using Randomization.com. Two persons unattached to the study will use the randomization generator and pack the 34 envelopes consecutive numbered from 1 to 34. A paper revealing the intervention group assigned will be placed in each envelope. A copy of the randomization list will be kept in a sealed envelope by the coordinating investigator until the study is completed.

The randomization envelopes will be used in numerical order.

After randomization the investigator writes the randomization-group on the neuromuscular blockade sheet (NMB sheet).

34 eligible patients will be randomized.

Blinding:

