Postoperative pain treatment with paracetamol, NSAID and morphine according to local guidelines.

PONV profylaxis:

I.v. dexamethason 8 mg routinely

Data collection

Perioperative data collection that will be noted in CRF:

Type of operation with operation code

Batch-number, expiration date, used and surplus quantities of rocuronium and sugammadex, TOF values (NMB sheet)

Body temperature measured immediately after intubation and again immediately before extubation

Size of hernia defect measured during operation just before the defect is sutured

Surgical ratings on 5 point scale

Operating time (from first incision to last suture)

Number of sudden abdominal contractions and episodes with “tight” abdomen

Need for additional NMB to optimize surgical conditions

Postoperative registration:

Number of patients with recurrences of hernias 2 years after herniotomy.

Statistics:

Eligible patients and excluded patients will be registered at a screening list.

Data from all randomized patients, who receive the intervention, will be included in the intention-to-treat analysis.

Patients, included in the intention-to-treat analysis, but who are categorized as major violation, will be excluded from the per-protocol analysis.

Normal distributed variables will be expressed by means and standard deviation; variables that are not normal distributed will be expressed by medians and interquartile range and the Mann-Whitney U test used for comparison of the median values.

Fisher's exact test will be used at comparisons of percentages. A p value < 0.05 is considered significant.

As the study is a crossover trial, it is necessary to test for a possible period effect and a treatment period interaction. To detect a possible period effect a two sample t test to compare the differences between the periods in the two groups of patients will be carried out. If there is no general tendency for patients to do better in one of the periods, we assume that the mean differences between the periods to be of the same size but with opposite signs.

To investigate the possibility of a treatment-period interaction a two sample t test will be carried out by noticing, that in the absence of an interaction, the patients response to the treatment will be the same regardless of the order in which it is received.

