If there is no period effect and no treatment-period interaction the analysis of the data regarding the primary outcome will be done by performing a Wilcoxon signed-rank sum test on all 34 patient's data (differences in workspace between the two treatments).

Primary outcome:

Improvement of surgical workspace estimated as the difference between the workspace (rated on a 5-point scale) during deep NMB and the workspace without NMB. Ratings are performed in the same patient during stable pneumoperitoneum at 12 mmHg.

Sample size calculation:

With a clinical relevant decrease of surgical workspace of 1 on the rating scale, an expected standard deviation of 2, type 1 error 0.05 and power 0.80, we calculated the sample size of 34 patients in total.

Up to 50 patients can be included to have an evaluable primary outcome in 34 patients.

Risks, side-effects and events:

Sugammadex: According to the Danish Medicine Agency's product summary, the side effects are as follows:

Very common (> 10%)	Taste disturbances.
Common (1-10%)	Anesthesia complication
Not common (0,1-1%)	Consciousness during anesthesia. Allergic reactions.

Laparoscopic herniotomy is done at Gentofte Hospital with an intraabdominal pressure at 12 mmHg without use of muscle relaxation for intubation and in some cases with use of bolus of muscle relaxation decided by the attending anesthetist. Patients allocated to group DEEP will receive rocuronium in a dose corresponding to a deep neuromuscular blockade (PTC < 8) after intubation. It is not regarded as a disadvantage to use large doses of muscle relaxation, since the effect is fully reversed by sugammadex at the end of surgery.

Registration of adverse events:

Patients will be observed during their stay at the hospital and will be contacted by telephone on first and seventh postoperative day. Possibly adverse events during this period will be reported. Finally the patient's case files will be reviewed for reports of adverse events at 17-21 days after operation.

The patients are encouraged to contact the local investigator, if they suspect any adverse events in connection with the trial and are treated according to applicable clinical principles and guidelines in the department.

Adverse events are registered as of the time when the patient is signing informed consent and the intravenous anesthetic is administered. All events are followed up until the final diagnosis or cause is established, and this is registered on the CRF.

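### The hypothesis asserts benefit on three secondary outcomes, and p < 0.05 applies to all seven secondaries with no gate and no exploratory label

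*Combined protocol and SAP*

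**What the plan says.** **Hypothesis.** One sentence covers four outcomes. Deep NMB "will give better surgical workspace, better surgical conditions, as well as shorter duration of surgery and reduced number of recurrences of hernias compared with no" blockade. Only the first, workspace, is the primary outcome; the other three are on the secondary list.

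**Outcomes.** The primary is the within-patient difference in workspace rating between deep NMB and no NMB. The next list is headed "Secondary outcomes: (comparing Group A with Group B") and has seven entries: conditions rating while suturing, operating time, a better/unchanged/worse judgement, sudden contractions, insufflator alarms, tight-abdomen episodes, and recurrence at two years.

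**Statistics.** Mann-Whitney is named for non-normal variables and Fisher's exact test for percentages. The threshold is the same throughout: "A p value < 0.05 is considered significant". The section contains no order of testing, division of alpha, dependence on the primary result or exploratory label, and neither does any other section.

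**Sample size calculation.** The calculation concerns workspace only: "type 1 error 0.05 and power 0.80, we calculated the sample size of 34 patients in total".

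**Publication.** Recurrence goes into a second paper, and further splitting of the data is allowed. Later papers are to carry the same trial registration number.

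**The concern.** A reader of the results will ask what a significant secondary outcome means. The plan's heading says that these outcomes are secondary, while its hypothesis sets three of them beside the primary as things the trial expects to show. Followed as written, the plan lets a single p < 0.05 on operating time, for example, be reported as significant support for part of the hypothesis even if workspace shows nothing. The secondaries are between-group comparisons of about 17 v 17 patients with no power statement. Recurrence will also be published apart from the primary result, so its readers may not see the two together. At stake is what the trial may say about conditions, duration and recurrence. The workspace conclusion is not at risk.

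**Working it through.** **Inputs from the documents**
- Threshold 0.05 for every test (Statistics).
- Three secondaries named in the hypothesis and seven listed in all (Hypothesis; Outcomes).
- Allocation: "Randomization is 1:1, and done using Randomization.com". With 34 patients this gives about 17 v 17.
- Effect: "clinical relevant decrease of surgical workspace of 1 on the rating scale"; spread: "an expected standard deviation of 2"; power 0.80 (Sample size calculation).

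**Assumptions, because the documents are silent**
- Tests are two-sided, and all null hypotheses are true.
- Test statistics are normal with a common correlation of 0, 0.5 or 0.8.

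**1. The plan's own figure.** Reading the SD of 2 as that of the within-patient differences:

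n = [2 × (1.960 + 0.842) / 1]² = 31.4, so 32 by the normal formula.

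The paired t version gives 33.4, so 34, with power 0.81 at 34. A one-sided test would give 25, and a two-sample comparison 63 per arm. The 34 therefore fits one two-sided paired test of workspace at 0.05. No allowance for other outcomes is built in, and that single test needs none.

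**2. At least one two-sided p < 0.05 among k secondaries.** For independent tests the chance is 1 − 0.95^k:
- k = 3: 1 − 0.857 = 0.143
- k = 7: 1 − 0.698 = 0.302

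For correlated tests the same probability comes from the equicorrelated normal model:

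| Correlation | Three in the hypothesis | All seven |
|---|---|---|
| 0 | 0.14 | 0.30 |
| 0.5 | 0.13 | 0.23 |
| 0.8 | 0.10 | 0.15 |

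With recurrence in its own paper, the main paper has six secondaries: 1 − 0.95⁶ = 0.265 if independent, 0.21 at correlation 0.5.

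**3. False claims of benefit only.** The hypothesis is directional, so only a result favouring deep NMB can appear to support it. That is 0.025 per two-sided test. For independent tests the chance is 1 − 0.975^k, which is 0.073 for three and 0.162 for seven.

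| Correlation | Three | Seven | Single test |
|---|---|---|---|
| 0 | 0.073 | 0.162 | 0.025 |
| 0.5 | 0.063 | 0.115 | 0.025 |
| 0.8 | 0.049 | 0.074 | 0.025 |

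**4. Discrete data.** Simulating 17 v 17 with Mann-Whitney and Fisher tests, under assumed recurrence of 10% or 15% and assumed event counts, gives these two-sided rates:
- The three: about 0.08 to 0.11, below the normal model at each correlation.
- The seven: about 0.25 to 0.26 if independent and 0.21 to 0.22 at a latent correlation of 0.5, again below the normal model. At 0.8 the rate is 0.16 to 0.18, slightly above it.

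Much of the fall for the three comes from Fisher's test. Its actual two-sided size at 17 v 17 is 0.001 at 5% recurrence, 0.008 at 10%, 0.016 at 15% and 0.020 at 30%.

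**The case against.** The strongest reply is that the plan has one powered primary outcome and lists the rest under a secondary heading, which most readers take to mean supportive. The type 1 error of 0.05 is stated for the primary's sample size. No family-wise target is set for the secondaries, and each is tested at about 0.05 or less. All of this stands. It shows that the plan is silent on how secondary claims are controlled. It does not remove the conflict with a hypothesis that asserts three of them.

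Some stronger readings are tempting, but the documents do not support them:
- *The trial's false-positive rate is 0.14 to 0.30 instead of 0.05.* The primary test keeps its own 0.05. The larger figures concern secondary claims only and count both directions. For false benefit on the three outcomes in the hypothesis, the rate is 0.05 to 0.07.
- *The plan declares the secondaries confirmatory.* It never uses the word. Nor does it say that a secondary result establishes the hypothesis if the primary fails. If the hypothesis is read as requiring all four benefits together, there is no inflation. The plan does not say which reading it intends.
- *Recurrence is the least protected claim.* Fisher's test makes it the most conservative comparison in the set.

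Seven can also be called a generous count. The conditions rating considers tightness and contractions, which are counted separately as well, and the better/unchanged/worse item re-rates the workspace change. Such overlap is a reason to look at the higher correlations, where the seven still give 0.15 two-sided.

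**Conclusion.** The point holds as a gap in how secondary claims are governed, and it is inexpensive to close. Three secondaries stand in the hypothesis beside the only powered outcome, one threshold covers all seven, and nothing gates or labels them. Under the assumptions above, the two-sided chance of at least one spurious significant secondary is two to three times the single-test 0.05 for the three in the hypothesis, and three to six times for all seven. Counted as false benefit against 0.025, the multiples are about the same, although the absolute rates are half as large or slightly more. The exact values depend on correlations that the documents do not give, and discrete data mostly lower them. No two-sided rate calculated for the three or the seven falls to 0.05. The validity of the primary analysis is not in question on this point.

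**What to change.** In Hypothesis, limit the confirmatory statement to workspace. In Statistics, limit the p < 0.05 significance claim to the primary test. State that all seven secondaries, including recurrence in its separate paper, are exploratory and will be reported with estimates and unadjusted 95% confidence intervals, without a claim of significance.

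If the sponsor wants confirmatory claims on conditions, duration or recurrence, it should write its own testing order into Statistics, starting from a significant primary result, and fix it before analysis. The documents give no basis for preferring one order over another. The timing matters because Ethical considerations describes routine unblinding after each operation.

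The cost is wording. Patients, data, procedures, the primary test and its power are unchanged. The one thing given up is that an isolated p < 0.05 on a secondary outcome can no longer be presented as confirming the hypothesis.

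### The period-effect test, as literally worded, tests the treatment effect and conflicts with the null hypothesis in the plan's next sentence

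*Combined protocol and SAP*

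**What the plan says.** Under Design, Group A has no NMB followed by deep NMB, and Group B has the reverse order. The Statistics section then sets out two preliminary tests.

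- **Period effect.** The procedure is "a two sample t test to compare the differences between the periods in the two groups of patients will be carried out". The sentence that follows describes the situation without a period effect: "we assume that the mean differences between the periods to be of the same size but with opposite signs".
- **Treatment-period interaction.** A second two-sample t test is announced, on the reasoning that response to treatment should not depend on order. The variable to be tested is not named.

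The primary analysis is tied to both: "If there is no period effect and no treatment-period interaction the analysis of the data regarding the primary outcome will be done" by a Wilcoxon signed-rank test on the differences in workspace of all 34 patients. No analysis is given for the case where either check is positive. The threshold throughout is "A p value < 0.05 is considered significant".

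**The concern.** The named procedure and the null hypothesis beside it do not match. A two-sample t test asks whether two group means are equal. The next sentence says that, without a period effect, the two mean period differences are equal in size and opposite in sign. If treatment works, those means are then unequal, and the t test should reject precisely when there is no period effect.

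The result decides whether the only specified primary analysis applies. On the literal reading, the better deep NMB works, the more often the plan leads to a branch for which it specifies nothing. Even as a purely descriptive check, the p value reported for the period effect would be a p value for treatment.

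**Working it through.** **Inputs**

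- Effect: "With a clinical relevant decrease of surgical workspace of 1 on the rating scale" (Sample size calculation).
- Spread: "an expected standard deviation of 2". The text does not say whether this is the SD of a rating or of the within-patient difference.
- Error rates: "type 1 error 0.05 and power 0.80". Two-sided testing is assumed.
- Size: "we calculated the sample size of 34 patients in total". Randomization is 1:1; an even 17/17 split is assumed.

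**Step 1: reproduce the plan's figure.** For a paired t test with SD of the difference 2, the noncentrality is (1/2) × √n. At n = 33 power is 79.5%. At n = 34 the noncentrality is 0.5 × √34 = 2.915 and power is 80.8%. So 34 is the smallest n reaching 80%, which supports reading SD 2 as the SD of the difference. A parallel-group formula gives 63 per arm and does not reproduce 34.

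**Step 2: what the stated contrast estimates.** Let D = period 2 minus period 1, τ = deep minus none, and π = the period shift.

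- Group A (none, then deep): E(D_A) = π + τ.
- Group B (deep, then none): E(D_B) = π − τ.
- As worded, A against B: (π + τ) − (π − τ) = 2τ. The period effect cancels.
- With the sign reversed in B: (π + τ) − (τ − π) = 2π. The treatment effect cancels.

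The condition in the plan's next sentence, E(D_A) = −E(D_B), is π = 0. That is the second contrast, not the first.

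**Step 3: how often the literal test declares a period effect when there is none (π = 0).** The difference in means is 2τ, with 17 per group and 32 degrees of freedom. The noncentrality is (2τ/SD) × √(17/2). At τ = 1 and SD 2 it is 1 × 2.915 = 2.915, and the rejection rate is 80.7%.

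| τ | SD of difference | Literal test declares a period effect |
|---|---|---|
| 1 | 2 | 80.7% |
| 0.5 | 2 | 29% |
| 1.5 | 2 | 98.9% |
| 1 | 1.5 | 96% |
| 1 | 2.5 | 62% |

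If SD 2 were instead the SD of a single rating, the SD of the difference is 2 × √(2(1 − r)). The rate is then 52%, 64%, 81% and 98% for within-patient correlations r of 0, 0.25, 0.5 and 0.75.

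**Step 4: simulation, 40,000 trials per scenario, SD 2.**

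| τ | π | As worded | Sign reversed |
|---|---|---|---|
| 1 | 0 | 81.0% | 5.1% |
| 0 | 1 | 4.9% | 80.6% |
| 1 | 1 | 80.5% | 80.9% |

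Rounding the differences to whole points changes little: 79.8% instead of 81.0% in the first row.

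**Step 5: effect on the route to the primary analysis.** At τ = 1, π = 0 and SD 2, a further 40,000 simulated trials gave the chance that the period check is negative and the signed-rank test is significant. It is about 1.4% with the contrast as worded and about 75% with the sign reversed. The interaction check is left out because its variable is unnamed.

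**The case against.** The strongest reply is that the two sentences belong together. The first says only that the differences are compared; it states neither a null of equality nor a sign convention. The second supplies the right null. A statistician who knows crossover trials would add the sign reversal and run a valid test, with about 5% false positives and about 81% power for a 1-point period effect. This stands: the plan does not unambiguously prescribe a treatment test, and 81% is not the error rate of every reasonable reading. But the only named procedure does not test the stated null, and the analyst should not have to choose between contrasts with opposite consequences once data are in hand.

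A reader might infer three stronger things that the documents do not support.

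- **That a real period effect would go unnoticed.** This holds only for this one test read literally. If the unnamed interaction variable were the deep-minus-none difference, the second test would be the sign-reversed contrast and would pick up a period effect. Moreover, with equal sequences an additive period effect does not bias the pooled estimate: the group means are τ + π and τ − π, which average to τ. It only adds spread.
- **That the plan withholds the primary analysis after a positive check.** It says what is done when both checks are negative and is silent otherwise.
- **That 81% is a fixed property of the design.** It depends on the assumed effect, SD and split, as Step 3 shows.

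Whether a primary analysis should hinge on preliminary tests at all is a separate question, and this point does not rely on it.

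**Conclusion.** Wrong as written. The algebra of Step 2 needs no assumption about SD or sample size: the period test as worded contrasts treatments and is inconsistent with the null stated directly after it. The size is conditional on following the sentence literally. At an effect of 1, SD of the difference 2 and 17 per sequence, a period effect is declared in about 81% of trials without one, against a nominal 5%. Over the values of effect and SD tried, the rate runs from 29% to 98.9%, always well above nominal. It matters because this check is one of two conditions for the only primary analysis the plan specifies, and the plan names no alternative.

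**What to change.** Amend the Statistics section in two places.

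1. **Period effect.** State that each patient's deep-minus-none difference is compared between Groups A and B by a two-sample test. Equivalently, compare the period differences after reversing the sign in one group.
2. **Treatment-period interaction.** State that each patient's sum (or mean) of the two ratings is compared between Groups A and B.

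The second change is needed with the first. If the interaction variable stays unnamed, it could be taken to be the deep-minus-none difference, and both checks would then be the same contrast.

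The cost is one or two sentences, with no additional patients, data or visits. The change should be made before any outcome data are examined by sequence.

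### The premise of the treatment-period interaction test holds only without a period effect, and the variable tested is not named, so a pure period shift can be reported as an interaction

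*Combined protocol and SAP*

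**What the plan says.** The trial is a two-sequence, two-period crossover: Group A is rated without NMB and then under deep NMB, Group B the other way round. The Statistics section plans two preliminary two-sample t tests.

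- **Period effect.** The t test is on the between-period differences. If patients do not generally do better in one period, the mean differences are taken to be equal in size and opposite in sign.
- **Treatment-period interaction.** The reason given is that "in the absence of an interaction, the patients response to the treatment will be the same regardless of the order". The wording is singular, one treatment and its order. The variable entering this t test is not named.

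Both results then act as a gate: "If there is no period effect and no treatment-period interaction the analysis of the data regarding the primary outcome will be done" by a Wilcoxon signed-rank test on all 34 patients. No analysis is given for the case where either test is positive. The significance rule is "A p value < 0.05 is considered significant".

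**The concern.** The no-period-tendency condition is attached to the period test only. The interaction premise carries no such condition, yet it needs one. If ratings drift between the first and second assessment for any reason, the response to a given treatment depends on when it was given, even with no interaction and no carry-over.

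Two things are at stake. First, reporting an interaction says that the benefit of deep NMB depends on the order of treatment, which is a different conclusion from a period shift. Second, a real carry-over check is relevant in this design: under Groups, the no-NMB rating in Group B follows rocuronium and sugammadex, whereas in Group A it follows only saline. A test built on the stated premise does not isolate that question.

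**Working it through.** **Inputs from the documents.** Effect: "With a clinical relevant decrease of surgical workspace of 1 on the rating scale". Spread: "an expected standard deviation of 2". Error rates and size: "type 1 error 0.05 and power 0.80, we calculated the sample size of 34 patients in total". Allocation: "Randomization is 1:1, and done using Randomization.com", with 34 envelopes.

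**Assumptions.** Two-sided tests, 17 per sequence, approximately normal ratings. The documents give no period shift, so I show 0.25, 0.5 and 1 point.

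**The plan's own figure.** For a paired comparison with difference 1 and SD of differences 2, the normal approximation gives ((1.96 + 0.84) × 2 / 1)² = 31.4, so 32. With the noncentral t, n = 33 gives power 0.795 and n = 34 gives 0.808. The stated 34 is reproduced, provided that SD 2 is the SD of within-patient differences. I use it in that sense below.

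**Expected values.** Let μ be the no-NMB mean in period 1, T the effect of deep NMB and π the shift in period 2, with no interaction or carry-over.

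| Variable | Group A | Group B | A minus B |
|---|---|---|---|
| Deep rating | μ + T + π | μ + T | π |
| No-NMB rating | μ | μ + π | −π |
| Deep minus none | T + π | T − π | 2π |
| Sum of both ratings | 2μ + T + π | 2μ + T + π | 0 |

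Only the sum (or mean) is equal in both orders when π is not zero.

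**Rate of false interaction calls.** For a between-group contrast D and standard deviation s, the noncentrality is D / (s × √(2/17)) on 32 degrees of freedom.

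- *Deep minus none*: D = 2π, s = 2. At π = 0.5 the noncentrality is 1 / (2 × 0.343) = 1.46.
- *Deep rating alone*: D = π. With an assumed between-patient SD of 0.7, s = √(0.7² + 2²/2) = 1.58.
- *Sum*: D = 0.

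| Shift π | Deep minus none | Deep rating alone | Sum |
|---|---|---|---|
| 0.25 | 0.11 | 0.07 | 0.05 |
| 0.5 | 0.29 | 0.15 | 0.05 |
| 1 | 0.81 | 0.43 | 0.05 |

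The single-rating column depends on the between-patient spread. For within-patient correlations from 0 to 0.75 it runs from 0.17 down to 0.08 at π = 0.5, and from 0.52 down to 0.17 at π = 1. Simulation (40,000 trials per setting, shifts 0, 0.5 and 1) agreed: 0.29 to 0.30 and 0.81 for deep minus none at 0.5 and 1 point, and 0.049 to 0.052 for the sum.

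**Relation to the period test.** In every simulated trial the t test on deep minus none gave the same decision as the period test with the sign reversed in one group. They are the same contrast.

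**Carry-over.** Add a carry-over λ to the second rating in Group B. The deep-minus-none contrast becomes 2π + λ, so shift and carry-over cannot be separated. With λ = 1 and π = −0.5 they cancel, and the simulated rejection rate was 0.049.

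**Power of the sum.** A carry-over difference of 0.5 changes the contrast in sums by 0.5. With between-patient SD 0.7, the SD of the sum is √(4 × 0.7² + 2²) = 2.44, giving power 0.09. With an assumed SD of differences of 1 it is √(4 × 0.7² + 1²) = 1.72, giving 0.13.

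**The case against.** The strongest reply is that the plan does not commit to a wrong test. It names no variable, and a loosely worded rationale followed by the usual comparison of sums or means fits the text; that test is unaffected by a period shift. This stands. A reader might infer that the plan will declare any period shift an interaction. The documents do not support that: the variable is open, and even on the literal reading the false call is a probability. What remains is a misstated premise plus an unnamed variable in a test that gates the primary analysis.

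The second reply is that little is added to the harm already done by the gate. This also stands. If the period test is correctly signed, the deep-minus-none test repeats it and blocks nothing more. If the period test is run without the sign reversal, it alone blocks the Wilcoxon test in about 0.81 of trials at the planned 1-point effect and SD 2; adding the interaction test at a 0.5-point shift raises this only to about 0.86. A test on one treatment's rating could add some blocking, which I have not sized.

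Third, a period shift is harmless to a balanced within-patient mean difference, but not under this plan, where a detected period effect already removes the only specified primary analysis. So one should not describe the plan as otherwise tolerating such shifts.

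Finally, nothing in the documents points to a large shift. Both ratings are made in the same patient at 12 mmHg, and 1 point equals the whole clinically relevant effect. The larger rates are therefore illustrations, not forecasts.

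**Conclusion.** The point holds in limited form. The premise is wrong as written, by algebra that needs no assumed figures beyond an additive period shift, and no nearby sentence repairs it. A test that follows it on deep minus none can report a pure period shift as an interaction in about 0.11 to 0.81 of trials for shifts of 0.25 to 1 point, against 0.05 for the sum. The sizes rest on 17 per sequence, two-sided 0.05, SD of differences 2 and assumed shifts. The single-rating figures also rest on an assumed between-patient SD.

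The consequence is a mislabelled finding and no usable check for carry-over. It is tempting to conclude that the misstated premise itself costs the trial its primary analysis. On the deep-minus-none reading with a correctly signed period test it does not, because the period test has already made the same decision.

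**What to change.** Two edits in the Statistics section.

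1. Replace the rationale and name the variable, for example: *If treatment and period do not interact, a patient's average rating over the two treatments has the same expectation in both sequences. The sum (or mean) of the two workspace ratings is compared between Group A and Group B by a two-sample t test and reported as a descriptive check.*
2. Delete the absence of a treatment-period interaction as a condition for the primary analysis.

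The second edit is needed. If the sum test were substituted but the gate kept, blocking of the primary analysis would rise from 0.05 to about 0.10 with no shift, and from 0.29 to about 0.33 at a 0.5-point shift (SD 2, correctly signed period test).

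The cost is a few lines of text and no extra data. The downside is low power, about 0.09 to 0.13 for a 0.5-point difference in sums, so the plan should say that a negative result is not evidence of no carry-over. These edits leave the period-effect condition in place; the lack of any analysis when that condition fails is a separate matter.
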